### **D.2. Planned Outcomes**

#### **Primary Outcomes:**

Primary outcomes are measured as event counts between baseline and 18 months after the beginning of study interventions using OCFS administrative data. We will treat all primary outcome events as integer count variables, with the exception of preventive services which will be treated as binary (services delivered / no services delivered). In the event that observed study outcomes are rare in the sample, we will treat primary outcomes as binary (occurred / did not occur) instead of treating rare outcomes as event counts.

The primary study outcomes (and variable class) are:

- Investigative Track OCFS maltreatment cases: event count
- Family Assessment Response (FAR) track OCFS cases: event count
- Total OCFS cases: event count as sum of investigative track and FAR track cases
- Indicated OCFS maltreatment investigations: event count
- Substantiated OCFS maltreatment investigations: event count
- OCFS foster care placements: event count
- Preventive services for families at risk of foster care: binary

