## **B. Treatment**

The project will enroll approximately 150 households in Monroe, Onondaga, and Westchester counties in New York state to receive \$500 per month, unconditionally, via a debit card over a one-year period, totaling \$6,000 per family. Another 300 will be assigned to the control group and will not receive the unconditional cash transfers but will be eligible to participate in research activities. Families will be eligible if they have a recently closed case managed by OCFS through their differential response system, called Family Assessment Response (FAR) in New York State. FAR is used for CPS reports that have been accepted by the New York State Central Register for Child Abuse and Maltreatment (SCR) where there is no safety concern that rises to the level of immediate or impending danger for the child and/or family. Often, families served in the FAR track have been referred for poverty-related social needs.

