## **C. Randomization and Participant Eligibility**

Households referred and determined eligible for Family Assessment Response (FAR) will be invited to participate in a randomized controlled trial of unconditional cash transfers. Approximately 150 individuals will be randomly assigned to the treatment group and will receive monthly \$500 unconditional cash transfers for one year. Another 300 will be assigned to the control group and will not receive unconditional cash transfers but will be eligible to participate in compensated research activities. We will randomly select 50 individuals per county into the treatment arm, and 100 individuals per county into the control arm.

Youth Research Inc. (YRI), an agency contracted by the New York Office of Child and Family Services (OCFS), will disburse treatment funds on a debit card. Longitudinal repeated measures will be collected through online surveys conducted before treatment begins, at 6 months after treatment begins, 12 months after treatment begins, and 18 months (6 months after treatment ends). Future maltreatment reports and case outcomes handled by OCFS will be measured using agency administrative data.

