### **Eligibility Criteria:**

To participate in this pilot, caregivers must meet the following eligibility criteria:

- Received an invitation from an OCFS caseworker to apply
- Have met the state eligibility requirements for the Family Assessment Response (FAR) program within the previous six months
- Live in Monroe, Onondaga, or Westchester County, New York
- Be 18 years of age or older at the time of application.

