## **D. Data, Study Sample, Outcomes, and Other Variables**

### **D.1. Data and Study Samples**

The study sample will be recruited from the population of eligible households in Monroe, Onondaga, and Westchester counties, New York. We will randomly select 50 households per county into the treatment arm, and 100 households per county into the control arm.

Data will be obtained from two sources:

1) A web-based survey for all study participants at baseline, at 6 months after treatment begins, at 12 months after treatment begins, and at 18 months after treatment begins (6 months after treatment ends). This survey will collect information on caretaker and child demographic, health, behavioral, educational, and social characteristics. All variables will be collected at baseline. We will repeat data collection for all time-varying variables at each post-baseline wave of the survey.

2) OCFS administrative records linked to the study participants and their children using the DOB and name of the study participant and all minor children in the participant's household. Data will be provided by OCFS as family-specific and child-specific counts of a series of events related to child maltreatment reports and agency interventions.

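### The preventive-services primary outcome has no new-start rule, so services already running at baseline can be scored as the outcome; separately, the eligibility passages disagree on whether the qualifying case must be closed.

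*Combined protocol and SAP*

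**What the plan says.** **Eligibility.** Section B: "Families will be eligible if they have a recently closed case managed by OCFS through their differential response system". The opening of Section C is wider: "Households referred and determined eligible for Family Assessment Response (FAR) will be invited to participate". The formal list in Section C asks that caregivers "Have met the state eligibility requirements for the Family Assessment Response (FAR) program within the previous six months". Neither part of Section C mentions closure or excludes families receiving services.

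**Outcomes.** Section D.2 sets the window: "Primary outcomes are measured as event counts between baseline and 18 months after the beginning of study interventions". Six of the seven primary outcomes are counts of cases, investigations or placements. The seventh is set apart: "with the exception of preventive services which will be treated as binary (services delivered / no services delivered". Any outcome that proves rare is also to be reduced to yes/no. Section C gives the intent: "Future maltreatment reports and case outcomes handled by OCFS will be measured using agency administrative data".

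**Data.** Section D.1: "Data will be provided by OCFS as family-specific and child-specific counts of a series of events". It describes no start, stop or determination dates. The participant characteristics in Section D.3 do not include an open case or current services at baseline.

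**The concern.** A case report has a date, so a window that opens at baseline can sort old reports from new ones. Service delivery runs over time. A service opened before baseline and still running is, on the plain words of D.2, delivered within the window. That family is a yes in either arm, and no effect of the cash on later need can change it.

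At stake is one of seven primary outcomes. Families fixed at yes pull the risk ratio toward 1, shrink the risk difference and raise its variance. If OCFS supplies only totals, carried-over services cannot be separated from new ones afterwards, so the definition has to be settled before the extraction is specified.

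The eligibility wording is a separate matter. As written, the formal list admits a family whose qualifying case is still open, and Section B does not.

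**Working it through.** **Inputs from the documents.** 50 treated and 100 control households in each of three counties (Sections C and D.1): 3 x 50 = 150 and 3 x 100 = 300, which agrees with the stated totals. Two-sided 0.05 (Section E.5). The plan gives no event rate, effect size or power for this outcome, so there is no planned figure to reproduce.

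**Assumptions, for scale only.** New-start risk 20% in control and 12% in treatment. A share q = 10%, 20% or 30% of families is in services at baseline, equal in expectation in both arms because of randomisation. In the new-episode calculation these families contribute no new episode. No covariates, county effects or multiplicity adjustment.

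**Formulas.** With p the new-start risk:

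- Carried-over services counted: observed risk = q + (1-q)p. The difference is (1-q)(p_C - p_T).
- New episodes only, all randomised families: risk = (1-q)p. The difference is again (1-q)(p_C - p_T).
- New episodes only, families not in services: risk = p, with sample sizes 300(1-q) and 150(1-q).
- z = difference / sqrt(r_C(1-r_C)/n_C + r_T(1-r_T)/n_T), where r is the risk analysed.

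**With nobody in services (q = 0).** 0.08 / sqrt(0.20 x 0.80/300 + 0.12 x 0.88/150) = 0.08/0.0352 = 2.27.

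**Worked case, q = 20%.**

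- Carried-over counted: risks 0.2 + 0.8 x 0.20 = 0.360 and 0.2 + 0.8 x 0.12 = 0.296. z = 0.064 / sqrt(0.36 x 0.64/300 + 0.296 x 0.704/150) = 0.064/0.0464 = 1.38.
- New episodes, all families: risks 0.160 and 0.096. z = 0.064 / sqrt(0.16 x 0.84/300 + 0.096 x 0.904/150) = 0.064/0.0320 = 2.00.
- Families not in services: 2.27 x sqrt(0.8) = 2.03.

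| q | Risks if carried-over services count (C v T) | Difference, points | Risk ratio | z, carried-over counted | z, new episodes, all randomised | z, not-in-services subset |
|---|---|---|---|---|---|---|
| 10% | 28.0% v 20.8% | 7.2 | 0.74 | 1.71 | 2.14 | 2.16 |
| 20% | 36.0% v 29.6% | 6.4 | 0.82 | 1.38 | 2.00 | 2.03 |
| 30% | 44.0% v 38.4% | 5.6 | 0.87 | 1.14 | 1.85 | 1.90 |

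The undiluted difference is 8.0 points and the undiluted ratio 0.12/0.20 = 0.60.

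Counting new episodes in all randomised families restores the ratio of 0.60 and most of the precision. It does not restore the 8-point difference, because families already in services still contribute nothing to it. The gain in z comes from the smaller standard error (0.0320 against 0.0464 at q = 20%).

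**A second scenario.** With new-start risks of 20% v 10%, power is 0.79 at q = 0. With carried-over services counted it is 0.55, 0.39 and 0.29 at q = 10%, 20% and 30%. With families already in services left out of this outcome it is 0.74, 0.69 and 0.62.

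**Count outcomes.** Here the question is one of wording. D.2 does not say whether an event is dated by report, opening or determination. A report made before baseline and determined after it could therefore fall inside or outside the indicated and substantiated totals. Under the rare-outcome fallback, one such event would fix the family at yes.

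**The case against.** The strongest case on the other side is that the plan's intent is clear and the damage may be small.

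- **The count outcomes.** A reader might infer that D.2 counts the qualifying FAR case itself as an outcome. The documents do not support this. The window opens at baseline and Section C speaks of later reports, so the FAR-track and total counts are probably already limited to new cases. The indicated and substantiated route is also thin: the qualifying case is on the FAR track, so a separate investigation would have to be pending at entry, or the track would have to change. The documents describe neither. What stands is that the dating rule is unstated.
- **Cause and effect.** A reader might infer that the loose eligibility wording produces the outcome problem. Nothing says that preventive services end when a FAR case closes, so settling eligibility would not settle the outcome. They are two points. The eligibility passages can also both hold, for a closed case whose FAR eligibility was met within six months; the fair complaint is that the formal list omits closure.
- **Prevalence.** Section B describes families without immediate or impending danger, and these services are for families at risk of foster care. Caseworker invitation may also limit enrolment of families in services. So q may be small. This stands: the documents do not give q.
- **Direction.** A reader might fear bias between the arms. Under randomisation q is equal in expectation, so there is no systematic imbalance and no inflated false-positive rate. This stands too.
- **The illustration.** The 20% v 12% scenario starts at z = 2.27, close to 1.96, so modest dilution looks decisive. At q = 30% the new-episode definition also falls short, at 1.85. The comparison between columns is more informative than the threshold.

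**Conclusion.** The concern holds in a limited form. The preventive-services outcome, as defined, can be met by services that began before treatment. Following the rule as written would then give a diluted answer on one primary outcome. The (1-q) shrinkage does not depend on the assumed risks, but its size rests on a q that the documents do not give. For q of 10% to 30% and 20% v 12% new-start risk, expected z is 1.71 to 1.14 as written, against 2.14 to 1.85 with new episodes in all randomised families.

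For the counts, the gap is confined to dating events, mainly in the indicated and substantiated totals. The eligibility passages conflict on closure and must be reconciled. The documents do not show how many families with open cases would enrol.

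**What to change.** 1. **Eligibility.** Reconcile Section B with both parts of Section C, so that one rule states whether the qualifying case must be closed at enrolment.
2. **Day 0.** Define it. The D.2 window starts at baseline but ends relative to the start of interventions.
3. **Preventive services.** Define the outcome as a new service episode opened after day 0, and say whether a second service opened while an earlier one is running counts as new. Analyse all randomised families, which keeps the intent-to-treat population of Section E.2. Take service status at day 0 from the same OCFS link and use it as a covariate, with the not-in-services subset as a sensitivity analysis. If no family in services can have a new episode, the covariate predicts the outcome perfectly in the logit model, and the plan should say how that is handled.
4. **Counts.** Date cases and investigations by report and placements by placement date, after day 0. A pre-baseline report determined later is then left out of the indicated and substantiated totals.

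**Cost.** Protocol and SAP wording, plus a request to OCFS for event and episode dates, or for counts already restricted by start date. Section D.1 describes only counts, so availability should be confirmed first. Event totals will be somewhat lower.

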## Secondary outcomes:

Secondary outcomes are related to child and family health, well-being, and stability. All outcomes are measured during each wave of survey data collection [baseline, 6 months, 12 months, 18 months]. For all measures derived from additive indices, we will treat measures as continuous. If the empirical distributions of additive indices are roughly symmetric, we will treat them as continuous real numbers. If the empirical distributions of additive indices are skewed, we will treat them as non-negative integers.

- Parental self-reported general health (19 physical health items derived from SF-36): items scored following RAND Corporation SF-36 scoring instructions for included questions. Additive index
- Mental health (Kessler 10 plus) Each item is scored from one 'none of the time' to five 'all of the time'. Scores of the 10 items are then summed, yielding a minimum score of 10 and a maximum score of 50. Additive index
- Stress and coping (Perceived Stress Scale - 4): Each item is scored from "never" to "all of the time" on a 5-point scale. Scores of 4 items are then summed, yielding a minimum score of 0 and a highest score of 16. Higher scores are correlated to more stress. Additive index
- Family dynamics and parenting (CHAOS): Each item is scored "yes" or "no". Scores of the items are then summed. The higher the score the higher the level of environmental chaos in the home. Additive index
- Parental Stress Scale: 18-item questionnaire assessing parents' feelings about their parenting role, exploring both positive aspects (e.g. emotional benefits, personal development) and negative aspects of parenthood (e.g. demands on resources, feelings of stress). Each item is scored on a 5-point Likert scale. Parental stress scores range from 18 to 90, with lower scores indicating lower levels of parental stress. Additive index
- Food insecurity: In the past four weeks, did you worry that your household would not have enough food? Binary
- Adult Hope Scale: 12 items scored on an 8-point ordinal scale. Additive index
- Child missed medical care: Parental yes/no report of any child in home with missed medical care in preceding 6 months. Binary
- Child truancy: Parental report of day of missed school for each child in the home aged 6-17 in the preceding 6 months. Ordinal [no missed days; 1-3 days; 4-6 days; 7-10 days; 11 or more days; child not enrolled in school]
- Hours per week of relative childcare: Parent-reported number of hours each week each child 0-5 spends receiving care from a relative other than a parent or guardian.
- Hours per week of non-relative child care: Parent-reported number of hours each week each child 0-5 spends receiving care from a non-relative. Non-negative continuous
- Hours per week of formal childcare: Parent-reported number of hours each week each child 0-5 spends receiving care in a day care center, preschool, or prekindergarten. Non-negative continuous
- Financial-well being (CFPB Financial Well-Being Scale: Each item is scored 0 to 4 and summed to a total following CFPB scoring instructions. Additive index.
- Housing instability: 3-items counting number of moves, rating home quality, and rating neighborhood quality. Additive index.

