### **E.2. Statistical specification**

Our primary analytic approach is an analysis based on the intent-to-treat principle that compares outcomes for those randomized into the treatment group to those who were randomized into the control group.

Our models account for time-stable heterogeneity across individuals and treatment sites using random intercepts for each individual enrolled in the study, for each time period during which surveys are collected, and for the county from which their qualifying OCFS case originated. These random effects adjust for correlation induced by repeated measurements of individuals over time, time period effects, and clustering of outcomes within counties.

Our regression models for outcome variable  $y$  take the following general form:

$$\mu = E(y|T, X) = \alpha_i + \delta_j + \gamma_k + \beta T_i + c_j T_i + \theta X_{ij}$$

$$\begin{pmatrix} \alpha \\ \delta \\ \gamma \end{pmatrix} \sim N(0, \Sigma)$$

Where  $T$  indicates selection into the treatment group,  $X$  is a matrix of demographic characteristics,  $i$  indicates an individual participant,  $k$  indicates county of residence at the time of study enrollment,  $j$  indicates survey time period,  $\alpha$  is a vector of individual-level intercepts,  $\delta$  is a vector of time period intercepts,  $\gamma$  is a vector of county-level intercepts,  $\beta$  is the time-stable component of the treatment effect,  $c$  is a vector of time-varying components of the treatment effect, and  $\theta$  is a vector of coefficients for demographic predictors.

The relationship between the treatment and outcomes of interest may vary as a function of time. We treat temporal relationships as potentially nonlinear, and model the relationship between time, treatment, and outcomes of interest using a series of time-period intercepts. We estimate a unique intercept for each treatment period as well as an interaction between treatment status and treatment period to capture time-varying effects of treatment.

For all continuous (additive index) outcomes with a roughly symmetric distribution, we treat the outcome as following a linear model where

$$y \sim N(\mu, \sigma^2)$$

For all binary outcomes, we treat the outcome as following a Bernoulli model

$$y \sim \text{Bernoulli}(p)$$

$$E(p|T, X) = \text{logit}^{-1}(\mu)$$

And for all count outcomes and additive index outcome with a non-symmetric distribution, we treat the outcome as following a negative binomial model

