$$y \sim \text{NB}(\mu, \psi)$$

$$E(y|T, X) = e^{\mu}$$

where  $\psi$  is a shape parameter.

The average treatment effect is identified as

$$\text{ATE} = E(y|T = 1, X) - E(y|T = 0, X)$$

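### Additive indices judged skewed go to a negative binomial model that cannot hold within-person variance below the mean; for short or left-skewed scales the treatment-by-period standard errors can be too large

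*Combined protocol and SAP*

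**What the plan says.** Section D.2, under secondary outcomes, gives three statements on additive indices. The first covers all of them: "For all measures derived from additive indices, we will treat measures as continuous". The next two split them by shape: "If the empirical distributions of additive indices are roughly symmetric, we will treat them as continuous real numbers", and "If the empirical distributions of additive indices are skewed, we will treat them as non-negative integers". Neither shape is defined. The section does not say which wave or arm is inspected, whether the inspection is blinded, or whether left skew counts.

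Section E.2 attaches the models. Roughly symmetric indices get a normal linear model. For the rest: "And for all count outcomes and additive index outcome with a non-symmetric distribution, we treat the outcome as following a negative binomial model". The link is logarithmic, and ψ "is a shape parameter". The models account for repeated measurement "using random intercepts for each individual enrolled in the study". They also include a separate intercept for each period "as well as an interaction between treatment status and treatment period to capture time-varying effects of treatment".

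After all three outcome models, E.2 defines the average treatment effect as E(y|T=1,X) − E(y|T=0,X). It does not say how a negative binomial fit is averaged over covariates and random effects to reach that quantity. No robust standard error is planned. Section E.4 refits the same models by MCMC with informative priors, so it does not test the choice of distribution.

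The stated ranges are 10 to 50 for the Kessler 10 and 18 to 90 for the Parental Stress Scale. For the PSS-4 the text is "yielding a minimum score of 0 and a highest score of 16".

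**The concern.** A questionnaire total with a floor and a ceiling is not an event count. The negative binomial starts at zero and has no upper limit. Given the person intercept, its variance is at least its mean. A bounded score can easily vary less than that within a person. The fitted model then assumes more noise than the data contain, and the excess enters the standard error of within-person comparisons, which the treatment-by-period terms are.

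Those terms may matter for interpretation. All indices are measured at baseline as well as at 6, 12 and 18 months. If baseline is one of the modelled periods, β carries any arm difference before treatment and the change from baseline sits in the treatment-by-period terms. The plan does not say which term or contrast is decisive.

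At stake is sensitivity to real changes in stress, mental health and family functioning. There is also a choice of model, and so of p-value, made after the outcome data are seen and by no stated rule.

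**Working it through.** **Figures in the plan.** The documents give no power, effect size, mean, SD, within-person correlation (ICC) or standard error for any index, so there is no stated figure to reproduce. They do give the allocation (3 × 50 = 150 treated, 3 × 100 = 300 control), four waves, the scale ranges above and the model. All means, SDs and ICCs below are assumptions, as are the ranges used for CHAOS (0-15) and the hope score (8-64).

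**Closed form.** With m = exp(μ), the model's variance given the random effects is m + m²/ψ, which is never below m. The true within-person variance is about w = (1 − ICC) × SD². If w < m, the fit drives ψ towards infinity (the Poisson limit). The standard error of a within-person contrast is then inflated by about √(m/w).

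- PSS-4, mean 6, SD 3, ICC 0.5: w = 0.5 × 9 = 4.5; √(6/4.5) = 1.15.
- PSS-4, mean 6, SD 3, ICC 0.7: w = 0.3 × 9 = 2.7; √(6/2.7) = 1.49.
- PSS-4, mean 12, SD 3, ICC 0.5 (left-skewed): √(12/4.5) = 1.63.
- K10, mean 20, SD 8, ICC 0.5: w = 0.5 × 64 = 32, above the mean, so the floor does not bind.

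**Simulation.** 200 null trials per setting; 150 against 300 participants; four waves; bounded integer scores; a random-intercept negative binomial fitted by maximum likelihood, with fixed wave effects and county omitted. The last three columns are the median model standard error divided by the empirical SD of the estimate. Monte Carlo error of a ratio is about 1/√(2 × 200) = 5%.

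| Scale (mean, SD), ICC | Skew | √(m/w) | Treatment × 18 months | Arm contrast at 18 months | Wave average |
|---|---|---|---|---|---|
| PSS-4 (6, 3), 0.5 | 0.34 | 1.15 | 1.16 | 1.06 | 1.00 |
| PSS-4 (6, 3), 0.7 | 0.34 | 1.49 | 1.50 | 1.12 | 1.01 |
| PSS-4 (6, 2.5), 0.5 | 0.29 | 1.39 | 1.39 | 1.13 | 1.00 |
| CHAOS (4, 3), 0.5 | 0.76 | 0.94 | 1.06 | 1.01 | 1.00 |
| CHAOS (4, 3), 0.7 | 0.76 | 1.22 | 1.19 | 1.00 | 0.96 |
| K10 (20, 8), 0.5 | 0.87 | 0.79 | 1.03 | 1.02 | 1.03 |
| K10 (20, 8), 0.7 | 0.87 | 1.02 | 1.02 | 1.02 | 1.01 |
| K10 (18, 6), 0.5 | 0.97 | 1.00 | 1.03 | 1.02 | 1.02 |
| K10 (18, 6), 0.7 | 0.97 | 1.29 | 1.28 | 1.10 | 1.03 |
| Parental Stress (38, 10), 0.5 | 0.56 | 0.87 | 1.02 | 1.00 | 1.01 |
| Parental Stress (38, 10), 0.7 | 0.56 | 1.13 | 1.15 | 1.03 | 1.01 |
| Hope (48, 9), 0.6 | −0.59 | 1.22 | 1.24 | 1.03 | 0.97 |

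Where √(m/w) is 1.13 or more, the nominal 5% interaction test rejected in 0.5% to 2.5% of null trials. The wave-averaged test rejected in 4.5% to 6% throughout.

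**Marked skew on the 0-16 scale.** Runs of 250 null trials looked at the treatment-by-12-month term. Right skew gave 0.98 (mean 4, SD 3, ICC 0.5, skew 0.81), 0.97 (mean 4, SD 3.5, skew 0.90) and 1.14 (mean 4, SD 3, ICC 0.7). A shorter 120-trial run of the first setting gave 1.16, a reminder of the noise. Left skew (mean 12, SD 3) gave 1.54, with 1.30 for the single-wave contrast. A further set of 100 trials per setting gave 1.5 to 1.6 for a left-skewed 0-16 score and 1.2 for a left-skewed hope-type score. It gave 0.9 to 1.1 for most clearly right-skewed settings, with 1.3 at mean 5, SD 2.5, ICC 0.6.

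**Linear comparison.** In simulated null trials of this design, a linear analysis of the same scores rejected in 4% to 6%.

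**The case against.** The strongest reply is that the switch is unlikely to apply where it does harm. A PSS-4 score with a mean near the middle of its range is close to symmetric: with scaled-beta margins and SD 3, skewness is +0.16 at mean 7 and −0.17 at mean 9. Such a score would probably stay in the linear branch. Clear right skew lowers the mean relative to the variance, so the floor often does not bind. This largely stands. It also weakens the PSS-4 rows in the table, whose skewness is only 0.29 to 0.34. It does not cover left skew, which the rule also sends to the negative binomial, nor strong within-person correlation (K10 at skew 0.97 and ICC 0.7 still gives 1.28). Because skewed is undefined, nobody can say in advance which scores would switch. The documents do not say that any scale is left-skewed.

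A second reply is that the inflation falls on one kind of contrast. That is right: the person-intercept variance adapts, so wave-averaged comparisons are essentially unaffected, and no section makes a treatment-by-period term the decisive test.

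A reader might also infer that the estimand changes from a mean difference to a ratio. E.2 does not support this, because the average treatment effect is a difference in expectations for all three models. Only the coefficients become log ratios.

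**Conclusion.** The point stands as a conditional weakness. The plan sends bounded scores to a variance model they can violate, on a shape check with no stated criterion, and no other section compensates. Under the assumed means, SDs and ICCs, the standard errors of the treatment-by-period terms are about 1.0 to 1.6 times the true value. Left-skewed 0-16 scores give the upper end and most clearly right-skewed settings lie near 1. Single-wave contrasts are affected less (1.00 to 1.13 in the table, 1.30 under marked left skew), and wave-averaged contrasts hardly at all (0.96 to 1.03).

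Three stronger readings are not supported. Standard errors are not wrong for every index. No single inflation factor can be given as a bound, since the closed form at SD 2.5 and ICC 0.8 for the PSS-4 reaches √(6/1.25) = 2.19. And no loss of power can be attributed to this trial, because the documents state neither an effect size nor a power target. The error is conservative, so it does not raise the false-positive rate, and it concerns secondary outcomes only. A change is worth making because it costs little and removes a data-dependent choice of model, coefficient scale and p-value.

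**What to change.** In D.2, remove the two sentences that split indices by shape and keep the statement that all are treated as continuous. In E.2, remove additive indices from the negative binomial sentence and keep that model for true event counts. State that every additive index is analysed with the linear mixed model and participant-clustered robust standard errors whatever its skew, and that mean differences are reported. This estimates the E.2 average treatment effect directly, so no averaging step from a log-link fit is needed.

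The cost is SAP wording only. The downside is possibly slightly less efficiency than a well-fitting skewed model would give. A bounded or ordinal model, named in advance for each index, can be kept as a sensitivity analysis.

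### Does listing non-enrolment as a sixth level of ordinal truancy, with no ordinal model in E.2, call for a change to the plan?

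*Combined protocol and SAP*

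**What the plan says.** Under Secondary outcomes in D.2, truancy is a "Parental report of day of missed school for each child in the home aged 6-17 in the preceding 6 months". Its class is "Ordinal [no missed days; 1-3 days; 4-6 days; 7-10 days; 11 or more days; child not enrolled in school": five rising bands of missed days, then a status. The plan does not say whether that status is ranked, excluded or reported separately.

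Section E.2 ties each distribution to a named class of outcome:

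- "For all continuous (additive index) outcomes with a roughly symmetric distribution, we treat the outcome as following a linear model"
- "For all binary outcomes, we treat the outcome as following a Bernoulli model"
- "And for all count outcomes and additive index outcome with a non-symmetric distribution, we treat the outcome as following a negative binomial model"

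Ordinal is not among them. E.2 defines the treatment effect as a difference in expected outcomes, which has no meaning for categories without scores. E.3 modifies the same regression for race, E.4 re-estimates the same models with priors, and E.5 deals with significance and multiplicity. None adds an ordinal model.

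The three childcare items are also reported per child, for example "Parent-reported number of hours each week each child 0-5 spends receiving care from a non-relative. Non-negative continuous". The random intercepts in E.2 are for participant, survey period and county.

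**The concern.** Read literally, the list ranks a child who is not enrolled above a child who missed 11 or more days. If the six categories are fitted in that order, one odds ratio combines two things that cash might change: whether a child is enrolled, and how much school an enrolled child misses. A reader could not tell which had moved.

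No model is named, so the coding and the model could be chosen after the data are seen, and the resulting p-value would then enter the multiplicity adjustment in E.5. The missing unit of analysis adds another free choice for four of the 14 secondary outcomes: children could be rows nested in participants, or be summarised per household. The plan does set a household rule for missed medical care, which counts any child in the home, so its absence for these four stands out.

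**Working it through.** **What the text supports.** The truancy list has 6 entries: 5 ordered bands plus 1 status. E.2 gives 3 model classes and no ordinal one. D.2 lists 14 secondary outcomes, of which 4 are per child. The plan states no power or effect figure for truancy, so there is nothing to reproduce. What follows is a conditional illustration.

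**Inputs.** From section B: 300 control and 150 cash households. Assumed, because the documents give no attendance or enrolment rates:

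- one school-age child per household, one wave, full response, no random effects;
- three spreads of missed days among enrolled children, in per cent: 25/30/22/13/10, 15/25/25/20/15 and 35/30/18/10/7;
- several non-enrolment rates by arm.

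**Model.** Proportional odds, logit P(Y ≤ k) = a_k − b·T, fitted by maximum likelihood to expected counts, with the standard error from the inverse Hessian. The odds ratio is exp(b); below 1 favours cash.

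**Check 1: six levels, identical attendance among enrolled children in both arms.** Ranges cover the three spreads.

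| Not enrolled, control vs cash | Six-level OR | SE(log OR) | z |
|---|---|---|---|
| 2% vs 1%, 3% vs 2% | 0.97 | 0.18 | −0.18 |
| 5% vs 2%, 8% vs 5%, 10% vs 7% | 0.909-0.912 | 0.176-0.179 | −0.53 |
| 10% vs 5% | 0.854-0.858 | 0.175-0.178 | −0.88 |

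For 8% vs 5% with the first spread, OR = 0.911 and SE = 0.177, so the 95% interval is exp(ln 0.911 ± 1.96 × 0.177) = exp(−0.093 ± 0.347), about 0.64 to 1.29. The five-level odds ratio among enrolled children is 1.00 in every case. So the six-level scale does pick up an enrolment difference, but weakly.

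**Check 2: five levels, when the extra enrolled children attend poorly.** Move 3 percentage points in the cash arm from not enrolled to 11 or more days, starting from 5%, 8% or 10%. The five-level odds ratio becomes 1.086-1.103, about 0.5 SE against cash. The six-level odds ratio is 0.978-0.989. Here the restricted scale makes a gain in enrolment look like harm.

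**Check 3: non-enrolment as its own binary outcome.** At 8% vs 5% the expected counts are 0.08 × 300 = 24 and 0.05 × 150 = 7.5.

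- OR = (0.05/0.95)/(0.08/0.92) = 0.61.
- SE(log OR) = √(1/24 + 1/276 + 1/7.5 + 1/142.5) = √0.186 = 0.43.
- The 3-point gap has SE √(0.08 × 0.92/300 + 0.05 × 0.95/150) = 0.024, or 2.4 points.

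A separate test would add a comparison to the E.5 adjustment and say little.

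**Unit of analysis.** The participant intercept in E.2 would already be shared by siblings entered as separate rows, so clustering within a family is partly covered. A further child-level intercept needs survey answers matched to the same child across waves. Section D.1 mentions children's identifiers only for record linkage ("OCFS administrative records linked to the study participants and their children using the DOB and name"), so the documents do not show that this is possible.

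**The case for a change.** The strongest case for a change is that it is cheap. A few sentences would name the model, fix the coding and set the unit, and would remove a choice that could otherwise be made with the data in view. The choice can also matter for direction: in Check 2 the two codings fall on opposite sides of 1. If non-enrolment is meant to be the worst level, the plan could say so.

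The description of the gap stands in full. The text is silent on all three points, and this is neither a redaction nor a reading error. What does not stand is that the gap does damage, or that there is a better rule to adopt. In Check 2 the odds ratios on either side of 1 are each within about half a standard error of it. Making the five bands the main scale would replace an intent-to-treat comparison with one restricted by a state that may itself respond to treatment, at a possible distortion as large as the one removed. At ages 6 to 17, ranking non-enrolment as the worst attendance state is a defensible composite. The childcare-hours items are neither ordinal nor affected by enrolment coding, so they add no weight to the truancy point. The plan does not say when these choices would be made; that they could follow sight of the data is possible, but not stated.

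**Conclusion.** No change to the plan follows. The missing model and unit are details that any analyst has to settle before fitting, and the ordinal label with the E.2 regression points to a cumulative-logit mixed model. The placement of non-enrolment is a fair trade-off: one coding mixes two effects, the other conditions on a post-randomisation state. Counts by category, arm and wave would let a reader see which had moved.

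The shift is about 0.2 SE for a 1-point enrolment gap, 0.5 SE for 3 points and 0.9 SE for 10% against 5%, too small to create a significant result alone. These figures rest on assumed attendance and enrolment rates and on one school-age child in each of 450 households. Families without a school-age child, or lost to follow-up, would make the real estimate less precise, while siblings and repeated waves would add information. The ordinal question concerns one secondary outcome and the unit question three more. The primary outcomes come from administrative records and are unaffected.
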